#### 2 PROTOCOL SYNOPSIS

STUDY NAME	CTPR-0014 Rev F March 7, 2017: A Multi-Center Retrospective- prospective Matched Pairs Cohort Study to Assess Clinical Outcomes of Lesions Treated with eBx Compared to Lesions Treated with Mohs Surgery
CO-PRINCIPAL INVESTIGATORS	[name] and [name]
SITES	Up to 5 sites will participate
STUDY DESIGN	This is a retrospective-prospective study design. Patients who completed treatment approximately 3 years (range of 2-4 years) at time of initial IRB approval of this study will be identified and any existing data in the patient's record will be collected in addition to conducting office visits for long-term follow-up. The study will include 2 parts:
	1. Retrospective chart review: Collect data from patient records who completed treatment a minimum of 2 years prior to study onset and determine the feasibility of doing a matched pair cohort study comparison of eBx versus Mohs surgery. The history, demographic and treatment data will be retrospectively collected from up to 320 subjects previously treated with eBx for the treatment of NMSC and up to 320 subjects previously treated with Mohs surgery for the treatment of NMSC.
	2. Prospective Follow-up: Patients will return for long-term follow-up visits for the investigators to assess the lesion site, document absence of recurrence/ absence of recurrence, toxicities, and collect patient reported outcomes.
SAMPLE SIZE	Up to 640 patients who will return for follow-up approximately 2 to 5 years post treatment so that at least 586 lesions have long term follow-up data collected. Follow-up may range from approximately 2 to 5 years post treatment. Up to 2 visits may be completed by each subject, one in 2016, and one in 2017-2018.
STUDY OBJECTIVES	
 
To evaluate local recurrence of eBx and Mohs treated lesions.
 
To evaluate toxicities related to eBx and Mohs treatments.
 
To evaluate cosmetic outcomes for lesions treated with eBx and Mohs.
 
To assess the ability to deliver therapy with eBx and Mohs treatment modalities.
 

PRIMARY ENDPOINT	Absence of local recurrence at approximately 3 to 5 year follow-up (range is approximately two to five years) at treatment site(s).

SECONDARY ENDPOINTS	
 
Comparison of long-term toxicities related to eBx vs. Mohs treatment;
 
Comparison of long-term cosmetic outcomes for lesions treated for NMSC with eBx vs. Mohs;
 
Comparison of Chronic toxicities;
 
Comparison of Patient Reported Outcomes (PRO) using a patient survey.
 
	
ESTIMATED STUDY PERIODFollow-up Visits #1: August 29, 2016 – August 31, 2017 Data Collection & Data Entry: August 29, 2016 – September 31, 20		
	Prospective Follow-up Visit #2: August 31, 2017- January 31, 2018 Data Entry: August 1, 2017 – February 28, 2018	
SPONSOR & FUNDING PARTY	Xoft – a subsidiary of iCAD, Inc. San Jose, CA	
STATISTICAL ANALYSESXoft – a subsidiary of iCAD, Inc. San Jose, CA		
STUDY MANAGEMENT	Eminence Clinical Research, Inc. Colorado Springs, CO	
ELECTRONIC DATA CAPTURE	Eminence Clinical Research, Inc. Colorado Springs, CO	
MEDICAL WRITING ASSISTANCE	Eminence Clinical Research, Inc. Colorado Springs, CO	

#### 4 INTRODUCTION AND BACKGROUND

More than one million skin cancer cases occur annually. Most of these forms of skin cancers are curable. Carcinoma is a medical word for a cancer that starts in a lining layer of cells such as the skin or the lining cells of the digestive system. There are many types of keratinocyte cancer, but two types of epithelial skin cancers are most common, basal cell carcinoma (BCC) and squamous cell carcinoma (SCC).

Epithelial skin cancer is a common neoplasm that affects more than a half of a million people each year. The most serious of skin cancers is melanoma, which was diagnosed in approximately 60,000 people in 2007. However, the majority of these lesions, estimated to be eighty to ninety percent, are basal cell cancers and the remainder is categorized as squamous cell.

Both types of malignancies are related to ultraviolet light exposure from the sun. Basal cell cancer begins in the lowest layer of the epidermis, the basal cell layer. About eight out of ten skin cancers are BCCs. They usually begin on areas exposed to the sun, such as the head and neck. BCC was once found mostly in middle-aged or older people, in the fourth decade of life and beyond. But now it is also being seen in younger people. This may be because people are spending more time in the sun without protecting their skin. BCC tends to grow slowly. It is very rare for a basal cell cancer to metastasize. But if left untreated, it can grow into nearby areas and spread into the bone or other tissues beneath the skin.

SCCs are more likely to spread into fatty tissues just beneath the skin. They are also more likely to spread to lymph nodes or to distant parts of the body than are BCCs, but this is not common. With thorough screening these neoplasms can be identified at an early stage. With the selection of the appropriate treatment option, these cancers can result in excellent local control with excellent cosmesis results.

There has been a diverse variety of modalities developed for the treatment of basal cell and SCC over the years, from surgical excision, to Mohs micrographic surgery, to radiation therapy. The location of the cancer and the extent of the disease effect the treatment options available to patients. The following section provides an overview of the different treatment modalities published in the literature.

Lovett et al reported on 339 patients who were consecutively treated for histologically confirmed basal cell (71%) and squamous cell (29%) carcinoma. A retrospective study was performed to assess local recurrence. The majority of the basal cell lesions (93%) and 97% of the SCCs were on the head. Radiation therapy was the initial treatment modality in 212 patients, and 127 patients were treated with radiation therapy after the initial surgical excision failed. Tumor control was analyzed by the type of external beam radiation therapy administered. The local control for superficial x-ray ranged from 91 to 100% reported categorically by tumor size. Electron beam ranged from 70 to 75% local control. Patients were stratified into groups by the

type of radiation beam used on the treatment. Excellent to good cosmesis was seen in 97% of the patients treated with superficial X-rays and in 78% of the patients treated with electrons, 78% of the patients treated with mixed beams, and in 80% of the patients treated with megavoltage photons. The overall complication rate (complications were defined as grade 4 toxicities) for the 310 patients whose data was available was 5.5%. Of the 217 previously untreated patients, the complication rate was 3.2%.

Silva et al report on a retrospective review of radiation therapy treatment for basal cell, squamous cell, and basal-SCC from 313 patients with 334 lesions treated. The objective of this study was to assess local control and late toxicities in patients treated with radiation therapy for the treatment of cancer of the pinna of the ear. For 270 patients, radiation therapy was the primary treatment, 50 patients received radiation therapy for recurrent cancer that had not previously undergone resection, and 12 patients received radiation therapy as an adjuvant treatment.

Orthovoltage X-ray radiation therapy (100-250 kV) was used in 83% of the patients, and electron radiation therapy was used in approximately 12%. The rest were treated with megavoltage X-rays (primarily  $^{60}$ Cobalt). The prescriptions were as follows: 17.5 Gy-20 Gy in one fraction, 35 Gy in five fractions with 7 Gy per fraction, 42-45 Gy in ten fractions with 4.2 to 4.5 Gy per fraction, and 50 to 60 Gy divided among 20 to 30 fractions with less than 3 Gy per fraction. Thirty-five (35) Gy was prescribed for 124 of the 313 patients. The follow-up ranged from 0.12 to 13.37 years. The primary endpoint was time to local failure, and the secondary endpoint was significant grade 4 late toxicities. Local control rate was reported to be 9% for patients who present with early stage cancer with tumor size 2cm or less in diameter. Orthovoltage X-ray radiation therapy has been shown to be efficacious primary treatment for squamous cell and BCC.

Chan et al report on a single center experience for the treatment of basal cell and SCCs. They studied 1005 lesions treated with single fraction radiotherapy. This retrospective chart review took place ten years later to allow for follow-up. All patients were treated with 45-100 kV X-ray. The radiation doses administered were 22.5 Gy, 20 Gy and 18 Gy. The 18 Gy prescription was reserved for patients who were considered frail or had very small tumors. The study endpoints were recurrence and late necrosis over a ten-year period. There was no difference in the recurrence rate for the group treated with 20 Gy versus 22 Gy, but there was a significant increase in late skin necrosis rate (p=0.002). Most tumors were in the head and neck regions. One subgroup in this study, patients who received radiation therapy for the treatment of cancer of the inner canthus of the ear, showed a higher recurrence rate because of the concavity, or standoff, of the treatment area. Chan concluded that a standoff of 0.5 cm-1.5 cm would cause the radiation dose to decrease by six to 23%.

Guix et al. published their series of 136 patients with basal cell or SCC of the skin of the face treated with surface molds and Ir-192 HDR brachytherapy with 98% 5-year local control rate with no severe early or late complications detected.

Other treatment options for patients with basal cell or SCCs include curettage, Mohs surgery and conventional surgery. Curettage has been said to be quick, requires minimal equipment, and is associated with a cure rate of 90% or better for select low-risk skin cancers. With this strategy, however, there is no margin control, and healing and cosmesis can be variable; moreover, it is not a very effective treatment for high-risk tumors and tumors in certain locations.

A common treatment for non-melanoma skin cancer (NMSC) has been Mohs surgery, which uniquely orients, maps, and processes removed tissue, permitting the microscopic evaluation of virtually 100% of the specimen margins. The completeness of this margin control permits the accurate identification and removal of all tumor extensions under the microscope. Tissues in Mohs surgery are processed as modified frozen sections which allow the accurate and rapid interpretation of most skin cancers. Cosmesis may be adversely affected and the process of care can be lengthy. For those patients where surgical resection is not an option, primary treatment with radiation therapy was selected for patients whose data will be collected in this study. The treatment approach was individualized based on specific risk factors, and patient characteristics for the most acceptable cosmetic and functional outcome.

#### 5 STUDY RATIONALE

Non-melanoma skin cancers, BCC and SCC, are the most prevalent of all skin cancers. Multiple publications have shown that radiation therapy using kilovoltage X-rays is a viable option for the treatment of BCC and SCC but treatment must be individualized to determine if radiation therapy should be an adjuvant therapy following surgical resection or if the radiation therapy is the primary treatment for skin cancer. Local recurrence rate varies depending on the histology, BCC versus SCC. SCC has a higher recurrence rate than BCC; deaths have been attributed to the recurrence of SCC.

Brachytherapy has the advantage of delivering a high dose to the tumor while sparing the surrounding normal tissues. With proper case selection and delivery technique, high-dose rate (HDR) brachytherapy has great promise, allows short treatment times, and can be performed on an outpatient basis. The Xoft Axxent Electronic Brachytherapy (eBx) System allows for the administration of high dose rate brachytherapy treatments using an electronic source. The Xoft Axxent System Controller and Source are cleared by the United States Food and Drug Administration to deliver high dose rate X-ray radiation for brachytherapy.

It is important to understand the recurrence rates and cosmesis for this treatment option. The rationale for this retrospective data collection study is to understand longer-term outcomes in

patients treated with eBx for the treatment of both BCC and SCC NMSC and how the outcomes compare to Mohs surgery outcomes.

#### 6 STUDY PURPOSE

The purpose of this retrospective-prospective study is to compare data after treatment for BCC or SCC NMSC with eBx to data after treatment with Mohs surgery in order to gain a better understanding of the clinical outcomes, cosmesis and durability, for this patient population.

#### 7 STUDY DESIGN, ENROLLMENT, AND DURATION

#### 7.1 Study Design

This is a retrospective-prospective study design. Patients who completed treatment approximately 3 years (range of 2-4 years) at time of IRB approval of this study will be identified and any existing data in the patient's record will be collected in addition to conducting office visits for long-term follow-up.

The study will include:

Identifying patients, retrospectively, who completed treatment a minimum of 2 years prior to study onset. The history, demographic and treatment data will be collected from up to 320 subjects previously treated with eBx for the treatment of NMSC and up to 320 subjects previously treated with Mohs surgery for the treatment of NMSC. Data will be collected from enough patients to achieve the required sample size of 293 lesions in each treatment group. Patients will then return for long-term follow-up visit for the investigators to assess the lesion site, document absence of recurrence, chronic toxicities, and collect patient reported outcomes.

#### 7.2 Sample Size

Up to 320 subjects treated with eBx and up to 320 subjects treated with Mohs surgery will have data collected retrospectively from the patient's medical records, and prospectively at the time of the follow-up visit for those who agree to participate in this study.

#### 7.3 Study Objectives

- i. To evaluate long-term local recurrence of eBx and Mohs treated lesions.
- ii. To evaluate long-term toxicities related to eBx and Mohs treatments.

iii. To evaluate long-term cosmetic outcomes for lesions treated with eBx and Mohs.

#### 7.4 Primary Endpoint

i. Freedom from local recurrence at the prospective follow-up visit in this study.

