#### 7.6.2 Exclusion Criteria

All answers must be NO to have lesions included in this study.

- 1. Target area is adjacent to a burn scar
- 2. Any prior definitive surgical resection of the cancer, prior to Radiation Treatment
- 3. Known perineural invasion
- 4. Actinic Keratosis
- 5. Known spread to regional lymph nodes
- 6. Known metastatic disease

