#### 8 METHODOLOGY

#### 8.1 Identifying the Population

The first phase of this study will be to identify patients who completed treatment with eBx or Mohs treatment approximately 3 years ago or more prior to study onset and collect history and demographic data, and eligibility and treatment planning and treatment data retrospectively from the patient records and on source worksheets to complete a matched pair cohort study comparison.

This phase will include a review of the site's patient medical records to determine if the source documentation contains the variables that are needed to determine eligibility and which will be used in the endpoint analyses. These variables include:

- Patient Age (within  $\leq 15$  year brackets)
- Pathology report for evidence of:
  - Lesion size (cm)
  - Lesion diagnosis (BCC, SCC)
- Last treatment date for each location
- Lesion location (e.g. face, extremities, neck, nose, scalp, torso)
- Toxicities at time of prospective follow-up visit

Matching will be performed according to:

- Calendar year of treatment for equivalent follow-up
- Patient age bracket [15-year brackets or less]
- Lesion diagnosis (BCC, SCC)
- Lesion size range (< 1 cm,  $\geq$ 1 and <2 cm,  $\geq$ 2 and <3 cm,  $\geq$ 3 and  $\leq$ 4 cm)
- Location according to the methodology below:
  - o Scalp
  - Face (includes neck)
  - o Nose
  - o Ear
  - o Torso
  - Upper extremities (Arms, hands, fingers)
  - Legs (Thighs, lower leg, feet, toes)

Data Collected Prospectively:

- Cosmesis rating by physician
- Cosmesis rating by the patient
- Recurrence of cancer
- Chronic toxicities
- Patient reported outcomes (PRO) survey

Patients who return for long-term follow-up will be required to provide informed consent for both the retrospective data and the prospective data that are collected at the time of the visit.

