#### **12 STATISTICAL CONSIDERATIONS**

#### 12.1 Data Collection

Data will be collected at the study site on case report forms and will be entered into the online database by ECR personnel. The following data collection requirements are listed below:

Form # and Name	Retrospective Chart Review	Prospective Follow-up and Data Collection
Demographics and History	Х	
Eligibility	Х	
Treatment Planning and Treatment	Х	
Follow-up Including Cosmesis, Chronic Toxicities, Recurrence		Х
Patient Reported Outcomes (PRO) Survey		Х

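### The primary endpoint is worded as recurrence status at the study visit, and no rule says that a local recurrence diagnosed and re-treated before that visit is a failure.

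*Combined protocol and SAP*

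**What the plan says.** Section 7.4 gives the primary endpoint as "Freedom from local recurrence at the prospective follow-up visit in this study". The synopsis words it as "Absence of local recurrence at approximately 3 to 5 year follow-up (range is approximately two to five years", at the treatment site. Neither adds that recurrences earlier than the assessment count.

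Section 8.1 puts recurrence of cancer in the list of prospectively collected data. It is absent from that section's list of chart variables, which are reviewed to see whether the "source documentation contains the variables that are needed to determine eligibility and which will be used in the endpoint analyses". In section 12.1, the case report form row "Follow-up Including Cosmesis, Chronic Toxicities, Recurrence" is marked in the prospective column only. Section 7.1 describes the retrospective data as history, demographic and treatment data.

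Section 7.1 enrols patients "who completed treatment a minimum of 2 years prior to study onset". Section 7.6.2 opens with "All answers must be NO to have lesions included in this study". Its nearest item concerns definitive resection before radiation, and no item in 7.6.1 or 7.6.2 concerns re-treatment after the index treatment.

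Section 12.2 sizes the study on a 1.5% historical 3-year recurrence rate for Mohs and a 2.5% non-inferiority margin, with 293 lesions per group. It names two-sided chi-square tests and gives no rule for recurrences that precede the visit.

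**The concern.** Any recurrence diagnosed in the first 2 years after treatment precedes every study visit. If it was re-treated successfully, the site is clear when the investigator examines it. Such a lesion can be enrolled, and on the literal wording of section 7.4 it meets the endpoint. Two sites, or two analysts, could score the same history differently and both claim to follow the protocol.

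The sizing rate is a proportion recurring over 3 years, whereas the endpoint reads as a status on one day. If re-treated recurrences go uncounted, the study measures something lower than the quantity it was sized on. The effect on the comparison depends on the truth and on the pattern of omission:

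- If eBx truly recurs more often and equal fractions are missed in both arms, the observed difference shrinks towards non-inferiority.
- If the true rates are equal, equal omission leaves the difference at zero and only narrows the interval.
- Unequal omission can favour either treatment.

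**Working it through.** **1. The passages side by side.**

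| Question | What the documents give |
|---|---|
| When is the endpoint assessed? | At the prospective visit (7.4); at about 3 to 5 years, range 2 to 5 (synopsis) |
| Where is recurrence named as data? | Prospective list (8.1); prospective column of the form table (12.1) |
| Can a recurrence precede the visit? | Yes: treatment ended at least 2 years before onset (7.1) |
| Can such a lesion be enrolled after re-treatment? | Yes: no criterion in 7.6 excludes it |
| Is it scored as a failure? | Not stated |

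**2. The plan's own figure.** Inputs from section 12.2: rate 0.015, margin 0.025, power 80%, alpha 0.05. I assume an equal rate for eBx and independent lesions.

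n = (z_alpha + z_power)² × 2p(1−p) / margin² = (1.645 + 0.842)² × 2 × 0.015 × 0.985 / 0.025² ≈ 292.4, rounded up to 293.

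This matches the plan with a one-sided 5% alpha. A one-sided 2.5% alpha would need 372. The illustration below therefore uses one-sided 95% bounds. The proposed definition changes no input, so 293 stands.

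**3. How sparse the events are.** Expected events per arm at the design rate: 293 × 0.015 = 4.4.

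Section 12.2 states no confidence-bound rule. Assume a Wald one-sided 95% upper bound on the difference (eBx minus Mohs), compared with 2.5 points: U = d + 1.645 × √[p₁(1−p₁)/293 + p₂(1−p₂)/293].

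| eBx / Mohs events | d (points) | SE (points) | U (points) | Against 2.5 | Uncorrected chi-square p |
|---|---|---|---|---|---|
| 7 / 4 | 1.02 | 1.12 | 2.87 | fails | 0.36 |
| 6 / 4 | 0.68 | 1.07 | 2.44 | passes | 0.52 |
| 6 / 3 | 1.02 | 1.02 | 2.69 | fails | 0.31 |

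Under this assumed rule, one uncounted eBx recurrence turns 7/4 into 6/4 and a fail into a pass. One uncounted Mohs recurrence turns 6/4 into 6/3 and a pass into a fail. Under the chi-square test that the plan names, none of the three is significant.

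**4. Range for an unknown fraction.** The documents do not say how many enrolled lesions were re-treated before the visit. Let m be the share of recurrences missed, equal in both arms, with true rates at the margin (eBx 4.0%, Mohs 1.5%). The observed difference is 2.5 × (1−m) points. The chance of wrongly declaring non-inferiority is Φ[(0.025 − d)/SE − 1.645], under the same assumed rule:

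| m (assumed) | Normal approximation | Exact binomial, same Wald rule |
|---|---|---|
| 0 | 5.0% | 6.9% |
| 10% | 7% | 10% |
| 25% | 13% | 18% |
| 50% | 37% | 44% |

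The table shows direction and sensitivity. It does not estimate what happens in this study.

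**The case against.** The strongest reply is that the time at which data are collected is not the window for events. A form completed at the visit can record any recurrence since treatment, so a prospective column does not show that earlier ones are lost. The chart-variable list in 8.1 is also weak evidence: it is introduced as what the variables include, and it contains toxicities at the prospective visit, which an existing chart cannot hold.

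Several passages favour a cumulative reading. Section 7.4 speaks of freedom from recurrence, section 7.3 aims at long-term recurrence, and sizing uses a 3-year rate. Section 7.1 says that "any existing data in the patient's record will be collected", and section 9 has patient-record data entered into the database. The case report form, which could settle the matter, is a separate document (15.2) and was not available.

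All of this stands, and it limits the claim. A reader might infer that recurrences before the visit will be lost, or will be scored as successes. The documents do not support that, because they leave capture possible. They do not require it, however, and even a form that records such an event needs a definition that makes it a failure.

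A reader might also infer that one such lesion would reverse the study's conclusion. That does not follow either. The tipping counts need a rule that section 12.2 does not state, and they depend on the method: 6 against 4 passes by Wald (2.44) but fails by Newcombe (2.69). Every threshold rule tips on one event somewhere. Against 4 Mohs events, the uncorrected chi-square test first reaches significance at 12 eBx events (p = 0.043).

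**Conclusion.** The point holds as a gap in the definition of the primary endpoint. The stated endpoint and collection schedule, followed literally, allow a recurred and re-treated lesion to count as recurrence-free. That is inconsistent with the 3-year recurrence rate behind the sample size. The cumulative reading is the more natural intention, but no passage makes it binding.

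The size is unknown, and the number of such lesions could be zero. What can be said is that about 4.4 events per arm are expected, so the handling of one or two lesions could matter if non-inferiority is judged by a confidence bound. That conclusion rests on the assumed Wald rule at one-sided 95% and on assumed missed fractions. It does not carry over to the chi-square test as written. This should be fixed; confidence is medium because the case report form was not seen.

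**What to change.** Use one definition in both the synopsis and section 7.4: a failure is any local recurrence at the treated site from the last treatment date through the study assessment, whether found in the chart or at the visit.

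Unless the case report form already does so, add recurrence (yes/no, date, re-treatment) to the retrospective chart review for both groups, and ask at the visit about recurrence treated elsewhere.

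The cost is one sentence in two places and, if needed, one chart item and one visit question. Charts are already under review, the last treatment date is already collected (8.1), and the sample size does not change. The drawbacks are that chart dates are less exact than visit findings, chart completeness may vary by site, and recurrences treated elsewhere depend on patient report.
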